11.0 EVALUATION DURING TREATMENT/INTERVENTION

Activity	Screening	Cycle 1 (± 3 days)		Cycle 2 (± 3 days)		Cycle 3 (± 3 days)		Cycles 4+ (± 3 days)		End of Treatment (within 7 days of decision to discontinue Treatment)	30-Day Follow- up (+ 14 Days)	Survival Follow- up (+14 days)
		Day 1	Day15	Day 1	Day15	Day 1	Day15	Day 1	Day15			
Informed consent	• ^a											
Demography	• ^a											
Medical History	• ^a											
Confirm Disease Diagnosis from fresh biopsy	• ^a											
Record Baseline Signs and Symptoms	• ^a	•										
Review and document IC/EC	• ^a											
Confirm patient continues to satisfy I/E Criteria			•									
Height	• ^a											
Physical Examination ^b	• ^a	•	•	•	•	•		•		•	•	
Weight	• ^a	•		•		•		•		•	•	
Vital signs ^d	• ^a	•	•	•	•	•		•		•	•	
ECOG PS	• ^a	• ^j		•		•		•		•	•	
Hematology and Chemistry ^e	• ^c	•	•	•	•	•		•		•	•	

Memorial Sloan Kettering Cancer Center
 [name]
 [name]

Activity	Screening	Cycle 1 (± 3 days)		Cycle 2 (± 3 days)		Cycle 3 (± 3 days)		Cycles 4+ (± 3 days)		End of Treatment (within 7 days of decision to discontinue Treatment)	30-Day Follow-up (+ 14 Days)	Survival Follow-up (+14 days)
		Day 1	Day15	Day 1	Day15	Day 1	Day15	Day 1	Day15			
Magnesium ^e	● ^a	●			●		●			●	●	
Coagulation (PT/INR/ aPTT) ^c	● ^c					●				●		
cfDNA ^o	● ^o									● ^o		
Hepatitis B surface antigen ^p	● ^a											
Hepatitis B Core Ab (total) ^p	● ^{a,h}											
Hepatitis C antibody ^h	● ^{a,h}											
Urinalysis ^{e, f}	● ^c	●		●		●		●			●	
Uric Acid	● ^c											
Pregnancy Test (urine or Serum) ^f	● ^c	● ^f		● ^f		● ^f		● ^f			● ^f	
Radiologic tumor assessments ^g	● ^a			Every 8 weeks (from C1D1) until Week 24, then every 12 weeks (± 1 week) ^g						● ^h	● ^h	
12-Lead ECG	● ^a	●				●				●	●	
ECHO	●	Every 12 weeks (from C1D1)								●		
ZW25 Administration		●	●	●	●	●	●	●	●			
AE and SAE assessments ⁱ	● ^{k,i}	● ⁱ	● ⁱ	● ⁱ	● ⁱ	● ⁱ	● ⁱ	● ⁱ	● ⁱ	● ⁱ	● ⁱ	
Record concomitant medications	● ^a	●	●	●	●	●	●	●	●	●	●	
Research blood collection ^m	● ^m	● ^m		●				● ^m				

Memorial Sloan Kettering Cancer Center
 [name]
 [name]

Activity	Screening	Cycle 1 (± 3 days)		Cycle 2 (± 3 days)		Cycle 3 (± 3 days)		Cycles 4+ (± 3 days)		End of Treatment (within 7 days of decision to discontinue Treatment)	30-Day Follow-up (+ 14 Days)	Survival Follow-up (+14 days)
		Day 1	Day15	Day 1	Day15	Day 1	Day15	Day 1	Day15			
Mandatory biopsy ⁿ	●									● only upon disease progression		
Survival Status ⁿ												● ⁿ

- a. Within 28 days prior to the start of Cycle 1, Day 1
- b. Directed physical examination is acceptable while on study treatment. Full examination is required at screening and the EOT visit.
- c. Within 14 days prior to the start of Cycle 1, Day 1
- d. Vital signs (blood pressure, pulse, respiration rate, and temperature) will be measured as outlined in the full protocol.
- e. Day 1 laboratory assessments may be performed up to 4 days prior to study agent administration. Laboratory results must be reviewed prior to each scheduled administration of ZW25, with the exception of coagulation testing (PT/INR, aPTT). In the event of severe toxicity, laboratory tests must be repeated as necessary until the toxicity resolves or stabilizes.
- f. For WCBP, a urine or serum pregnancy test will be performed at screening, prior to dosing on Day 1 of every cycle (it can be performed up to 14 days prior to Day 1) and at the 30-day Follow-Up visit. Additional testing may be performed in accordance with institutional requirements or local regulation.
- g. Patients will complete tumor assessments every 8 weeks (from C1D1) until Week 24, then every 12 weeks (± 1 week). If a patient discontinues prior to documentation of PD, a tumor assessment is to be performed at the End of Study visit or 30-Day Follow up visit, if not performed within the previous 6 weeks. Patients who have discontinued study treatment for reasons other than PD will be followed per RECIST 1.1 every 12 weeks (±3 weeks) until documentation of PD, starting a subsequent anti-cancer therapy or for up to one year from Cycle 1, Day 1, whichever comes first.
- h. As clinically indicated.
- i. All AEs and SAEs from the time of informed consent should be recorded.
- j. ECOG assessment is not necessary on Cycle 1 Day 1 if screening assessment was performed within 3 days prior
- k. For logistical reasons such as holidays, a +/- 3 day window applies to all study visits.
- l. Mandatory biopsy at screening and EOT (at time of progression of disease) within 14 days of EOT before initiating new treatment regimen.
- m. Research bloods include ADA and cfDNA sample collection. Research bloods can be collected at screening or cycle 1 day 1 before initiating treatment for baseline collections.

ADA will be collected at baseline and pre-dose at cycles 2, 4, 6, 8, 12, 18, 24 Day 1.

- n. Survival status' can be documented with a phone call or any clinic visits.
- o. CfDNA will be collected at screening or cycle 1 day 1 before initiating treatment for baseline collections and again at End of Treatment
- p. Hepatitis B Testing, if not done previously at MSK to rule out active infection (see exclusion criteria for details)

Memorial Sloan Kettering Cancer Center
 [name]
 [name]

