14.0 BIOSTATISTICS

14.1 Populations for Analyses

All treated population: all treated patients regardless if they completed cycle 1 or the amount of drug received.

Efficacy population: All treated patients except patients without a post baseline assessment of response will be excluded.

Sample Size

This study aims to assess the activity of ZW25 in advanced HER2 overexpressing endometrial cancers and carcinosarcomas as measured by the best overall response rate as determined by RECIST 1.1. Assuming we use a binary endpoint of response, defined as best overall response of CR or PR versus not (best overall response \leq 24 weeks from the start of treatment), a sample size of 25 patients provides 90% power to test the hypothesis that the response rate is promising (defined as 30% or higher) against a non-promising rate of 10% or lower. This calculation is based on historical data from studies with ineffective agents in a similar patient population, which have ORR $<$ 10% and PFS rate at 6 months $<$ 20%,^{7,49-51} and uses a two-stage minimax Simon design, with Type I error=10%. Sixteen patients will be enrolled in the first stage and if 1 response is observed among the 16 the study will end for lack of activity. If \geq 2 responses out of 16 are observed, the study will continue to stage 2, where an additional 9 patients will be enrolled for a total of 25. At the end of the study, if at least 5/25 responses are observed then this will be considered a positive study (i.e. conclude that ORR is $>$ 10%).

Based on historical accrual rates in similar populations, and with the increased prior lines of therapy that will not be allowed for eligibility, we anticipate successful enrollment of 2 patients per month yielding a total accrual time of 18 months. Accrual will continue until 25 evaluable for efficacy response patients are treated (i.e. 25 patients in efficacy population as defined above).

Sensitivity analysis for ORR will include in the calculation of ORR patients who do not have post baseline assessment of response as failures.

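### The calendar gives two rules for the discontinuation scan, and for patients who stop before Week 8 that scan can decide whether they stay in the primary ORR denominator

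*Combined protocol and SAP*

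**What the plan says.** **The scan (Section 11.0 calendar).** The label of the radiologic tumor assessment row carries footnote g. The cells of that row under End of Treatment and 30-Day Follow-up carry footnote h.

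- Footnote g: "If a patient discontinues prior to documentation of PD, a tumor assessment is to be performed at the End of Study visit or 30-Day Follow". An exemption applies to this scan: "if not performed within the previous 6 weeks". The footnote then asks for RECIST follow-up every 12 weeks (±3 weeks) after a stop for reasons other than PD, until PD, new anti-cancer therapy or one year from Cycle 1 Day 1.
- Footnote h: "As clinically indicated".
- The calendar has no End of Study column. Its column is End of Treatment.

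**Timing.** Screening imaging may be up to 28 days before Cycle 1 Day 1 (footnote a). On-study scans are every 8 weeks to Week 24. The 30-Day visit falls 30 days (+14) after the last treatment (Section 10.0).

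**The denominator (Section 14.1).** The efficacy population is defined as "All treated patients except patients without a post baseline assessment of response will be excluded". Accrual runs until 25 patients are in that population. A sensitivity analysis for ORR counts patients with no post-baseline assessment as failures.

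**Related text.** Section 13.2 treats every patient who received at least one dose as evaluable. Section 12.0 says that a patient who discontinues ZW25 must also come off the study.

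**The concern.** One scan is required by one footnote and discretionary by the other, and nothing says which prevails. The 6-week waiver adds a second gap, because it does not ask that the earlier scan be post-baseline.

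This matters only for a patient who stops before any on-study scan, in practice before Week 8. Anyone already scanned at Week 8 is in the denominator. For the early stopper, a scan at discontinuation means counting as a non-responder unless it shows a response. With no scan then or later, the patient leaves the efficacy population and is replaced. The primary ORR and the rule of at least 5 responses in 25 would then be applied to a group partly selected by whether imaging was done. If those who drop out are mostly failures, the false-positive risk exceeds the 10% that the plan allows.

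**Working it through.** **1. The plan's own figures.** On power, Section 14.1 states that "a sample size of 25 patients provides 90% power to test the hypothesis that the response rate is promising (defined as 30% or higher". The null is given as the comparison "against a non-promising rate of 10% or lower". On design, the calculation "uses a two-stage minimax Simon design, with Type I error=10" percent. For stage 1: "if 1 response is observed among the 16 the study will end for lack of activity", read here as 0 or 1 responses, since the study continues at 2 or more. The study is positive at 5 or more of 25.

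P(positive | p) = Σ over x = 2 to 16 of P(X₁ = x) × P(X₂ ≥ 5 − x), with X₁ ~ Bin(16, p) and X₂ ~ Bin(9, p).

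At p = 0.10:

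| Stage 1 responses | Probability | Chance of reaching 5 | Product |
|---|---|---|---|
| 2 | 0.2745 | 0.0530 | 0.0145 |
| 3 | 0.1423 | 0.2252 | 0.0321 |
| 4 | 0.0514 | 0.6126 | 0.0315 |
| 5 or more | 0.0170 | 1 | 0.0170 |

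The sum is 0.0951. At p = 0.30 the same formula gives 0.903. An exhaustive search found no design with fewer than 25 patients that meets 10% error and 90% power. The stated design is correct.

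**2. How far the waiver reaches.** Six weeks is 42 days.

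- Screening scan the day before Cycle 1 Day 1: the waiver runs to about Day 41.
- Screening scan 28 days before: 42 − 28 = 14, so to about Day 14.
- Last dose on Day 15: the 30-Day visit is at Day 45 or later, outside the waiver even with the most recent screening scan.
- Single dose on Day 1: the 30-Day visit is at Day 31 to Day 45. The waiver can cover both visits only if the screening scan was within about 42 − 30 = 12 days before dosing and the visit is not late in its window.

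The waiver can therefore remove the scan at both visits only for about a single-dose patient with a recent screening scan.

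**3. Effect of dropping and replacing.** Let u be the share of treated patients with no post-baseline assessment. The documents give no value for this trial, so u is assumed. Further assumptions are that all these patients are non-responders, that none is scanned later, and that both stages count efficacy-population patients. With an all-treated ORR of 0.10, the rate in the efficacy population is q = 0.10 / (1 − u), and the rule in step 1 is evaluated at q.

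| Dropped | q | P(positive) |
|---|---|---|
| none | 0.1000 | 0.095 |
| 1 of 26 | 0.10 × 26/25 = 0.1040 | 0.108 |
| 2 of 27 | 0.10 × 27/25 = 0.1080 | 0.122 |
| 10% | 0.10 / 0.90 = 0.1111 | 0.133 |
| 20% | 0.10 / 0.80 = 0.1250 | 0.190 |

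At the success boundary, 5/25 is 20.0%. With one or two further treated patients counted as failures it is 5/26 = 19.2% or 5/27 = 18.5%.

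**The case against.** **The footnotes may not conflict.** The row label carries g, so h could be meant for patients whom g does not oblige, such as those with PD already documented or a scan within 6 weeks. A mislettered superscript is also possible: the biopsy row carries the survival-status letter, although a separate biopsy note exists. This is fair, but the two cells that staff will follow still show h, and no text gives g precedence.

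**The discontinuation scan is not the only planned one.** A reader might infer that clinical discretion alone decides who is counted. The documents do not support that. Footnote g also plans 12-weekly imaging after a non-PD stop, and Sections 1.0, 4.2 and 10.0 continue scans until PD, death or new therapy. This is a real backstop, but a partial one. It ends at new therapy, and it conflicts with Section 12.0, which takes the patient off the study.

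**The size could be overstated.** A reader might take the Section 3.6 figures, 34 evaluable of 43 treated (21% not evaluable) and 48 of 67 (28%), as the likely loss. That would give 0.197 and 0.258. Those counts come from another, ongoing study. The documents do not say why the remaining patients were not evaluable, and nothing ties them to missed discontinuation scans.

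**The direction is not certain.** A declining patient may go unscanned, or may be the very patient in whom imaging is indicated. The documents do not settle this, which is why non-response among dropped patients is stated as an assumption. Losses for PFS are limited as well, since death is an event.

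**The effect is disclosed.** The Section 14.1 sensitivity analysis counts unscanned patients as failures. That stands, but the accrual target is set in the efficacy population and the sensitivity analysis has no role in the 5/25 decision.

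**Conclusion.** The point holds as a wording conflict with a bounded effect on the primary endpoint. Footnotes g and h give different rules for the same scan, the waiver does not require a post-baseline scan, and Section 14.1 makes a post-baseline assessment the condition for being counted.

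With one or two unscanned patients, the false-positive probability at an all-treated ORR of 10% is 0.108 or 0.122 against 0.095. At 10% dropped it is 0.133. These figures rest on an assumed loss rate, non-response in every dropped patient and no later scan.

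The inflation itself comes from the Section 14.1 exclusion and its conflict with Section 13.2. The footnotes only influence how many patients meet that exclusion. A reader might infer that correcting them returns the error to 0.095. It would do so only if every affected patient were then scanned. The sample size and decision rule are not in error.

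**What to change.** In Section 11.0:

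1. Have the End of Treatment and 30-Day radiology cells cite footnote g in place of h.
2. Reword the waiver so that only a post-baseline tumor assessment in the previous 6 weeks satisfies it.
3. Replace the End of Study visit in footnote g with End of Treatment, the name of the calendar column.
4. Reconcile the off-treatment imaging in footnote g with the Section 12.0 statement on leaving the study.

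The cost is protocol wording, plus one standard CT for the few very early stoppers whose screening scan no longer satisfies the waiver. Footnote g already requires nearly all the other scans.

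This reduces avoidable exclusions. Patients who die or withdraw before a scan would still be dropped and replaced, so Sections 13.2 and 14.1 also need to be reconciled on who is in the primary denominator.

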1.0 PROTOCOL SUMMARY AND/OR SCHEMA

[figure not shown]
This is a Phase 2, open label study designed to evaluate the efficacy and safety of ZW25 in patients with advanced/recurrent HER2 overexpressed endometrial cancers and carcinosarcomas. Up to 25 patients will be enrolled on this study.

The study will be conducted in two stages. Stage 1 will accrue 16 patients and if two or greater responses are seen, Stage 2 will accrue an additional 9 patients. In this study the recommended ZW25 dose will be 20mg/kg intravenously (IV) every two weeks. Treatment cycles will be 28 days.

Patients will continue to receive study treatment until they present with progressive disease (PD) per Response Evaluation Criteria in Solid Tumors (RECIST) version 1.1, develop unacceptable toxicity or withdraw consent, whichever comes first, or until the study is terminated.

Tumor assessments, including radiological assessments by computerized tomography (CT) or magnetic resonance imaging (MRI) scans are performed at Screening and subsequently every eight weeks (from Cycle 1 Day 1) for the first 24 weeks and then every twelve weeks until PD, death or initiation of subsequent anti-cancer therapy, whichever occurs first. All patients who discontinue study treatment for any reason are followed every 3 months until death, lost to follow up, or withdrawal of consent, for survival follow up for up to 2 years.

Figure 1: Study Schema

Abbreviations – IV: intravenous, ORR: Overall response rate, PFS: Progression-free survival, OS: Overall survival, CBR: Clinical benefit rate, DOR: Duration of response

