All patients who discontinue study treatment for any reason will be proceed onto survival follow up. Patients will be followed up for survival status every 3 months (from End of treatment visit) for 2 years until death, lost to follow up or withdrawal of consent.

Exploratory Correlative Studies

1. Anti-drug antibodies (ADA) will be assessed at baseline (baseline ADA can be collected on C1D1 pre dose) and pre-dose at Cycles 2, 4, 6, 8, 12, 18, 24 Day 1. The immunogenicity testing will be performed using validated assays in 3 steps as follows: screening assay (Tier 1), confirmation assay (Tier 2), and titration (Tier 3). Only samples positive in the screening assay will be tested in confirmation and further titrated to determine the titer of ADA.

At each timepoint, 5mL of blood will be collected into a red top tube and processed as follows:

- Invert 5x
- Clot at least for 30 minutes
- Separate serum within 30-60 minutes of collection
- Centrifuge 1000-2000 x g at 4c for 15-20min
- ~1.25mL serum into each 2mL cryovial

Storage: Store at -70° F/-80° F (storage at -20° F acceptable) for up to 1 month. Ship frozen on dry ice monthly. Blood samples for ADA will be processed and stored at the Immune Monitoring Facility (IMF) until batch shipment to Zymeworks, Inc.

Memorial Sloan Kettering Cancer Center
[name]
[name]

2. To explore the molecular associations between the *HER2* biomarkers: gene amplification (by NGS and ISH), protein overexpression by immunohistochemistry (IHC) and mutational status and/or copy # variations of relevant cancer-related genes using MSK-IMPACT platform in all patients and to determine mechanisms of underlying response and resistance.

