12.0 CRITERIA FOR REMOVAL FROM STUDY

Discontinuation of Study Treatment Due to Adverse Events

If ZW25 is discontinued, the patient must be discontinued from the study. Study treatment should not be resumed in the case of the following treatment-related events.

- \geq Grade 3 cardiac event
- Other non-hematologic events of Grade 4 severity
- Failure to meet re-treatment criteria within one cycle due to insufficient recovery from a treatment-related toxicity. In such cases, continuation of study treatment may be considered for those patients who have experienced clinical benefit if agreed upon by the Principal Investigator.

Removal of the Patient from the Study or from Study Drug Administration

The patient or legally authorized representative is free to withdraw consent and discontinue participation in the study at any time without prejudice to further treatment.

Patients will be removed from the study treatment when their disease worsens, and there is no clinical benefit. Additionally, a patient's participation in the study may be discontinued at any time at the discretion of the Investigator. The following may be justifiable reasons for the Investigator to remove a patient from the study:

- The patient suffers an intolerable adverse event
- Non-compliance, including failure to appear at one or more study visits
- The patient was erroneously included in the study
- The study is terminated.

If a patient or the patient's legal guardian(s), acting on behalf of the patient, discontinues participation in the study, or the patient is discontinued by the Investigator, the reason for discontinuation must be captured in the eCRF. Any AEs experienced up to the point of discontinuation must be documented on the AE eCRF. All serious adverse events (SAEs), and those AEs assessed by the Investigator as at least possibly related to study drug should continue to be followed until they resolve or stabilize, whichever comes first.

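### For patients who stop ZW25 before progression, the imaging rules conflict; footnote g can date progression late and may leave no scan near Week 24

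*Combined protocol and SAP*

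**What the plan says.** Section 1.0 gives the main schedule. After a baseline scan, imaging is repeated "subsequently every eight weeks (from Cycle 1 Day 1) for the first 24 weeks and then every twelve weeks until PD, death"; starting another anti-cancer therapy also ends it. Sections 4.2 and 10.0 give the same intervals and end points. Stopping ZW25 is not one of those end points, and there is no calendar cap.

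The Section 11.0 table and footnote g repeat these intervals from C1D1, with a ±1-week window. Footnote g then adds a rule for patients who stop for reasons other than PD. They are "followed per RECIST 1.1 every 12 weeks (±3 weeks) until documentation of PD, starting a subsequent anti-cancer therapy or for up to one year", the year being counted from C1D1. The starting point of the 12 weeks is not given. Footnote g also calls for a scan at the end-of-study or 30-day visit, "if not performed within the previous 6 weeks". In the table, however, the End of Treatment and 30-Day cells for that scan carry footnote h, which leaves it to clinical indication.

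Section 12.0, under its heading on discontinuation for adverse events, states: "If ZW25 is discontinued, the patient must be discontinued from the study". Section 10.0 says otherwise: "All patients who discontinue study treatment for any reason will be proceed onto survival follow up", and "Patients will be followed up for survival status every 3 months (from End of treatment visit) for 2 years".

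**The concern.** No text says which rule governs. The main text does seem to intend scanning off drug. Section 5.1 prohibits other cancer treatment during study treatment, so ending scans at the start of new therapy mostly describes patients who have already stopped ZW25.

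Under footnote g the imaging becomes sparser because the patient stopped drug, for example after a fall in LVEF, a Grade 4 toxicity or a Grade 4 infusion reaction. Any delay or loss of readings then depends on the reason for stopping. The 24-week PFS rate needs a reading near Week 24, and PFS and DOR depend on when PD is detected. ORR is best response within 24 weeks, so it is exposed only if a first or confirming response scan is missed.

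**Working it through.** **1. The plan's design figures.** Inputs (Section 14.1): continue if at least 2 of 16 respond, positive if at least 5 of 25, p0 = 0.10, p1 = 0.30.

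P(positive | p) = Σ over x = 2 to 16 of P(X = x; 16, p) × P(Y ≥ max(0, 5 − x); 9, p).

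This gives 0.0951 at p = 0.10 and 0.9030 at p = 0.30. An exhaustive search returns the same minimax design, so the stated 10%, 90% and 25 patients reproduce. The scan conflict does not alter them.

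**2. The rules side by side, for a patient off drug without PD.**

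| | Sections 1.0, 4.2, 10.0 | Section 11.0, footnote g | Section 12.0, literal |
|---|---|---|---|
| To Week 24 | every 8 weeks | every 12 ± 3 weeks | none |
| After Week 24 | every 12 weeks | every 12 ± 3 weeks | none |
| Ends | PD, death, new therapy | PD, new therapy, one year from C1D1 | on stopping |

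Before Week 24 the interval itself differs. After Week 24 the first two rules differ only in the window (±3 against ±1 week) and the one-year cap.

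**3. Is there a scan at Week 24 ± 1 under footnote g?** Assumptions: stopping at Weeks 2, 4, …, 22 (11 times); scans due up to the stop have been done; baseline is Week 0; the ±1 window applies at Week 24. A ±3 shift moves all off-drug scans together.

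| 12 weeks counted from | No shift: stop times with no scan at 24 ± 1 | Shift −3 / +3 |
|---|---|---|
| C1D1 | 0 of 11 | 11 / 11 (scan at Week 21 / 27) |
| last scan | 8 of 11 (next scan Week 28 or 32) | 7 / 7 |
| stop date | 10 of 11 (next scan Weeks 26 to 34) | 7 / 9 |

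Example with a last-scan anchor: a patient stops just after the Week 16 scan. The next scan is due at 16 + 12 ± 3 = Weeks 25 to 31, against Week 24 on the main schedule.

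The scan at stopping was placed on the stop date. There it is never triggered in these 11 cases, because the last scan is at most 6 weeks old. If it is done at the 30-day visit (30 to 44 days, or 4.3 to 6.3 weeks, after the last dose), single rows change in both directions:
- Last dose Week 18, last scan Week 16: the visit falls at Weeks 22.3 to 24.3, more than 6 weeks after the scan, so a scan near Week 24 can result.
- Last dose Week 2: the visit falls at Weeks 6.3 to 8.3. With a last-scan anchor, the next scans are at Weeks 18.3 to 20.3 and 30.3 to 32.3, so the Week 24 scan is lost.

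The counts are illustrations over stop times, not expected shares of patients.

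**4. Delay in dating PD.** If PD falls uniformly within a scan interval, the mean delay is half the interval: 8/2 = 4 weeks, 12/2 = 6 weeks, and 15/2 = 7.5 weeks at the top of the window.

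**5. Censoring.** Section 14 censors PFS and DOR at last follow-up, not last scan. Take a stop at Week 16 under footnote g. Scans end by Week 52, while survival contacts run to 16 + 104 = Week 120. If a survival contact counts as follow-up, up to 120 − 52 = 68 unscanned weeks could count as progression-free.

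**6. ORR, illustration only.** Section 13.1 requires a repeat scan at least 4 weeks after a CR or PR. A PR first seen at Week 16 is rechecked at Week 24 on the main schedule, but possibly after Week 24 under footnote g. The documents give no share of responses lost. If 5%, 10% or 20% of true responses went unread or unconfirmed, the effective rate would be 0.30 × 0.95 = 0.285, 0.30 × 0.90 = 0.27 or 0.30 × 0.80 = 0.24. The formula in step 1 then gives power of 0.873, 0.837 or 0.742.

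**The case against.** The best defence is that the texts can largely be read together. The Section 12.0 sentence sits under an adverse-event heading, while Section 10.0 keeps stopped patients for an end-of-treatment visit, a 30-day visit and survival follow-up. It is probably loose wording for leaving treatment. Footnote g, counted from C1D1 with no shift, keeps the Week 24 scan, and its scan at stopping fills some gaps. ORR and CBR need no scan at Week 24, and the confirmation requirement in Section 13.1 has no exception for patients off drug. A cap on off-drug scanning can be a legitimate choice.

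Much of this stands, and it limits the size of the point. It does not remove the conflict. Footnote g names no anchor, and a permitted 3-week shift moves even a C1D1-anchored scan out of 24 ± 1. The scan at stopping is required by one footnote and discretionary under another. The cap contradicts three sections and is not matched by the censoring rule.

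**Conclusion.** The imaging rules conflict in current text and must be reconciled. Before Week 24, footnote g lengthens the nominal interval from 8 to 12 weeks (15 at the top of the window) for patients who stop without PD. It can date PD late and, depending on the unstated anchor, may leave no scan near Week 24. The 24-week PFS rate, PFS and DOR are mainly affected.

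Three stronger readings are tempting but not supported:
- That Week 24 status will go unread. This is certain only under a literal Section 12.0, which Section 10.0 and footnote g contradict; under footnote g it depends on anchor and window.
- That the main text scans every 8 weeks until PD. It does so only to Week 24.
- That the primary endpoint is shown to be biased. ORR suffers only if a response scan is actually missed, and the documents do not show how often that would happen.

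The documents give no rate of stopping before PD, so the number of patients affected cannot be stated. The scan counts rest on the assumed stop times and anchors, the delays on uniform PD timing, and the power figures on assumed losses.

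**What to change.** - Rewrite footnote g to apply one C1D1-anchored schedule on and off drug (8-weekly to Week 24, then 12-weekly, ±1 week) until PD, death or new anti-cancer therapy, in line with Sections 1.0, 4.2 and 10.0.
- If the sponsor keeps a one-year cap, state it in all of these sections and censor PFS and DOR at the last adequate tumor assessment.
- Make the footnote on the End of Treatment and 30-Day scan cells agree with footnote g.
- Reword Section 12.0 so that stopping ZW25 does not end tumor and survival follow-up. The criteria for stopping treatment are not touched.

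The cost is protocol wording and a few scans in patients who stop before PD, which the main text already requires. Sample size and decision rule stay as they are.
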